4.0 SELECTION AND ENROLLMENT OF PARTICIPANTS

4.1 General Eligibility Criteria

4.1.1 Inclusion Criteria

- 4.1.1.1 Ability and willingness of participant (or legally authorized representative) to provide informed consent prior to initiation of any study procedures.
- 4.1.1.2 Individuals ≥ 18 years of age.
- 4.1.1.3 Documentation of laboratory-confirmed SARS-CoV-2 infection, as determined by a molecular (nucleic acid) or antigen test from any respiratory tract specimen (e.g., oropharyngeal, NP, or nasal swab, or saliva) collected ≤ 240 hours prior to study entry and conducted at any US clinic or laboratory that has a Clinical Laboratory Improvement Amendments (CLIA) certification or its equivalent or any non-US DAIDS-approved laboratory.
- 4.1.1.4 Participants must be expected to begin study treatment no more than 7 days from self-reported onset of COVID-19 related symptoms or measured fever, where the first day of symptoms is considered

symptom day 0 and defined by the self-reported date of first reported sign/symptom from the following list:

- subjective fever or feeling feverish
- cough
- shortness of breath or difficulty breathing at rest or with activity
- sore throat
- body pain or muscle pain/aches
- fatigue
- headache
- chills
- nasal obstruction or congestion
- nasal discharge
- loss of taste or smell
- nausea or vomiting
- diarrhea
- documented temperature $>38^{\circ}\text{C}$

4.1.1.5 One or more of the following signs/symptoms present within 24 hours prior to study entry:

- subjective fever or feeling feverish
- cough
- shortness of breath or difficulty breathing at rest or with activity
- sore throat
- body pain or muscle pain/aches
- fatigue
- headache
- chills
- nasal obstruction or congestion
- nasal discharge
- nausea or vomiting
- diarrhea
- documented temperature $>38^{\circ}\text{C}$

4.1.1.6 Oxygenation saturation of $\geq 92\%$ obtained at rest by study staff within 24 hours prior to study entry. For a potential participant who regularly receives chronic supplementary oxygen for an underlying lung condition their oxygen saturation should be measured while on their standard home oxygen supplementation level.

4.1.1.7 Agrees to not participate in another clinical trial for the treatment of COVID-19 or SARS-CoV-2 during the study period until reaching hospitalization or 28 days post-entry, whichever is earliest.

- 4.1.1.8 Additional inclusion criteria as appropriate for the investigational agent (see relevant appendix/appendices).

4.1.2 Exclusion Criteria

- 4.1.2.1 History of or current hospitalization for COVID-19.
- 4.1.2.2 For the current SARS-CoV-2 infection, any positive SARS-CoV-2 molecular (nucleic acid) or antigen tests from any respiratory tract specimen (e.g., oropharyngeal, NP, or nasal swab, or saliva) collected >240 hours prior to study entry.
- 4.1.2.3 Current need for hospitalization or immediate medical attention in the clinical opinion of the site investigator.
- 4.1.2.4 Use of any prohibited medication listed in [section 5.4.1](#) within 30 days prior to study entry.
- 4.1.2.5 Receipt of convalescent COVID-19 plasma or other antibody-based anti-SARS-CoV-2 treatment or prophylaxis at any time prior to study entry.
- 4.1.2.6 Receipt of other available investigational treatments for SARS-CoV-2 at any time prior to study entry. This does not include drugs approved for other uses and taken for those uses.
- 4.1.2.7 Known allergy/sensitivity or any hypersensitivity to components of the investigational agent or placebo. See relevant appendix.
- 4.1.2.8 Any co-morbidity requiring surgery within 7 days prior to study entry, or that is considered life threatening in the opinion of the site investigator within 30 days prior to study entry.
- 4.1.2.9 Additional exclusion criteria as appropriate for the investigational agent (see relevant appendix/appendices).

4.2 Study Enrollment Procedures

All sites will be registered through the DAIDS Protocol Registration Office (DAIDS PRO) at the Regulatory Support Center (RSC) by PPD.

Prior to implementation of this protocol, and any subsequent full version amendments, each site must have the protocol and the protocol consent form(s) approved, as appropriate, by the institutional review board (IRB)/ethics committee (EC) and any other applicable regulatory entity (RE) responsible for oversight of the study.

Upon receiving final approval, PPD on the site's behalf will submit all required protocol registration documents to the DAIDS PRO at the RSC. The DAIDS PRO will review the submitted protocol registration packet to ensure that all of the required documents have been received.

Site-specific informed consent forms (ICFs) will be reviewed and approved by the DAIDS PRO, and sites and PPD will receive an Initial Registration Notification from the DAIDS PRO. A copy of the Initial Registration Notification should be retained in the site's regulatory files.

For amendments, sites will receive a notification letter from PPD with instructions to sites prior to implementation. Upon receiving final IRB/EC and any other applicable RE approvals for an amendment, sites should provide the necessary approvals to PPD.

PPD will submit amendment registration packets to the DAIDS PRO at the RSC on behalf of the sites. The DAIDS PRO will review the submitted protocol registration packet to ensure that all required documents have been received. For full version protocol amendments, sites must receive the initial registration notification for the amendment from the DAIDS PRO prior to implementing the amendment. Site-specific ICF(s) will be reviewed by the DAIDS PRO if the site ICF was not submitted as part of the prior registration.

Sites and PPD will receive an Amendment Registration Notification when the DAIDS PRO receives a complete registration packet. The first notification will be based on receipt of minimal document requirement, which allows sites to start the implementation of the amendment. A final notification will be sent to sites and PPD once the entire registration packet review has been completed. A copy of the Amendment Registration Notification should be retained in the site's regulatory files.

For additional information on the protocol registration process and specific documents required for initial and amendment registrations, refer to the current version of the DAIDS Protocol Registration Manual.

4.2.1 Protocol Activation

PPD will be responsible for site activation for both ACTG and non-ACTG sites.

4.2.2 Randomization

Participants who meet the enrollment criteria will be randomized to the study through the IRT (Interactive Response Technology) system.

4.3 Co-enrollment Guidelines

Co-enrollment in an observational study or the ACTG REPRIEVE study (ACTG 5332) is allowed and does not require permission from the A5401 protocol chairs, as long as

ACTG network blood collection limits are not exceeded, that is, 450 mL over 8 weeks.

Co-enrollment in an interventional study following hospitalization for COVID-19 or after 28 days post-entry (Day 29 onward) for the treatment of COVID-19 or its complications is allowed.

For specific questions and approval for co-enrollment in other studies, sites should follow the directions described in the [Study Management section](#).

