5.4.1 Prohibited Medications

Use of hydroxychloroquine (unless used chronically for autoimmune diseases),

chloroquine (unless used for a parasitic infection), ivermectin (unless used for a parasitic infection), any antibody-based therapy for COVID-19, remdesivir, fluvoxamine (unless used chronically), and HIV protease inhibitors (unless used chronically for HIV infection) while on study, prior to hospitalization. In the event of hospitalization, these medications may be given unless otherwise specified in the agent-specific appendix/appendices.

See relevant appendix/appendices for additional prohibited medications, if applicable.

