6.2.3 Post-Entry Evaluations

On-Treatment/Post-Treatment Evaluations

Evaluations should occur in the visit windows described in [Tables 6.1-1](#) and [6.1-2](#).

Study Completion Evaluations

Participants will be evaluated at week 24 or later, depending on the agent-specific appendix.

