6.3.11 Study Diary

Participant-Completed Study Diary

Participants will be asked to keep a log of symptoms, medications they are taking for COVID-19 symptoms, and major events such as urgent visit to an emergency room or clinic and hospitalization in their study diary. This log will be completed on paper or electronically, if appropriate electronic systems are available.

At study entry, participants will complete the study diary with site staff prior to initiating investigational agent/placebo. Participants will be asked to complete subsequent entries per the SOE. The diary should be completed at approximately the same time every day.

If the day 28 visit occurs on study day 28, then the day 28 study diary may be completed with the site staff during the day 28 visit, otherwise it should be completed by the participant on study day 28.

Study Diary Reminder and Staff Review of Study Diary

Participant will be contacted every day on days 1-28 and reminded to complete their study diary. This reminder may be by telephone, text message, email, or other method for which the participant provides permission. A direct response from the participant is not required.

The study diary will be reviewed by study staff in person or remotely with each participant according to the schedule in [Tables 6.1-1](#) and [6.1-2](#). If an appropriate electronic system is available, the participant's diary entries will automatically be captured in the eCRF. If such a system is not available, the study staff will record the participant's answers on the study diary eCRF. If the participant uses a paper

diary and it is feasible, prior to or during the remote study visits, sites will ask the participant to send images of each of their study diary entries to be reviewed at the next study contact. See MOPS for requirements for timely eCRF entry of diary data.

Participants who report worsening symptoms from any cause during the trial may be referred to their health care provider or closest emergency room. Such instances will be recorded at the time of the notification, and during follow-up to assess study endpoints, i.e., hospitalization or death.

Retrieval of Study Diary

If the participant uses a paper diary, the study diary should be collected following the current Diary Completion Guidelines on the A5401 PSWP. See MOPS for additional instructions on retrieval of Study Diary.

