6.3.13 Virologic Studies

Anterior nasal (**Phase III only**) and NP swabs (**Phase II only**) will be collected for quantitative SARS-CoV-2 RNA, performed in near real-time.

Influenza and other respiratory viral testing may be performed on stored NP swabs.

Additional information can be found in the MOP and the LPC.

Self-Collected Anterior Nasal Swabs (Phase III)

Participants will self-collect anterior nasal swabs. Participants will be instructed by study staff and will obtain the day 0 swab while observed by study staff. This swab should be collected prior to the first dose of investigational agent.

After Day 0, in phase III, nasal swabs will be self-collected by the participant on their own. Remote-collected nasal swabs will be stored at home as per the MOP.

Retrieval of Self-Collected Nasal Swabs (Phase III)

Site staff will retrieve the nasal swabs collected by the participants at home as per the MOP and LPC. The swabs will be processed, stored, and shipped to the central laboratory as per the LPC.

Staff-Collected NP Swab (Phase II only)

NP swabs will be collected during in-person visits. At study entry, the sample should be collected prior to the first dose of investigational agent.

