10.2.1 Phase II: Primary Outcome Measures

10.2.1.1 Clinical (Symptom Duration): Duration of targeted COVID-19 associated symptoms from start of investigational agent (day 0) based on self-assessment. Duration defined as the first of two consecutive days when any symptoms scored as moderate or severe at study entry (pre-treatment) are scored as mild or absent, AND any symptoms scored as mild or absent at study entry (pre-treatment) are scored as absent. The targeted symptoms are feeling feverish, cough, shortness of breath or difficulty breathing, sore throat, body pain or muscle pain or aches, fatigue (low energy), headache, chills, nasal obstruction or congestion (stuffy nose), nasal discharge (runny nose), nausea, vomiting, and diarrhea. Each symptom is scored daily by the participant as absent (score 0), mild (1), moderate (2) and severe (3).

10.2.1.2 Virologic: At each of days 3, 7, 14, and 28, quantification (<LLoQ versus \geq LLoQ) of SARS-CoV-2 RNA from site-collected NP swabs.

10.2.1.3 Safety: New Grade 3 or higher AE through 28 days.

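### Co-enrollment in another COVID-19 treatment study opens on Day 29, but the phase II Day 28 NP swab and the Day 28 blood samples may be collected up to Day 32, so they can follow another trial's treatment

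*Protocol*

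**What the plan says.** **When the bar ends.** Under Protocol 4.1.1.7 the participant agrees to stay out of other COVID-19 treatment trials "during the study period until reaching hospitalization or 28 days post-entry, whichever is earliest". Section 4.3 matches this: co-enrollment in an interventional study "after 28 days post-entry (Day 29 onward) for the treatment of COVID-19 or its complications is allowed".

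**When the Day 28 specimens are taken.** Section 6.2.3 states "Evaluations should occur in the visit windows described in" Tables 6.1-1 and 6.1-2. In both tables the window row gives the Day 28 visit plus four days, with no allowance for an early visit. For phase II, section 6.3.13 adds "NP swabs will be collected during in-person visits", so the swab date is the visit date. Inflammatory and coagulation markers, stored plasma and stored serum are also due at Day 28 in both phases, and PBMCs at selected sites in phase II.

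**What the swab is used for.** Section 10.2.1.2 defines the phase II primary outcome: "Virologic: At each of days 3, 7, 14, and 28, quantification" of RNA against the LLoQ. The same swab supplies the Day 28 RNA level and the last point of the RNA area under the curve (10.2.3.7 and 10.2.3.8).

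**What is fixed to the day.** Section 6.3.11 foresees a late visit for the diary: "If the day 28 visit occurs on study day 28, then the day 28 study diary may be completed with the site staff". If the visit falls later, the participant completes that diary entry alone on Day 28. The staff-collected swab has no matching rule.

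**The concern.** The 28-day bar on other treatment trials covers the period in which the primary outcomes are measured. It ends by the calendar, while the Day 28 specimens end with a visit that can come later. A participant and a site can follow every stated rule and still produce a Day 28 swab or blood sample after another trial's agent has been given.

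Such a result partly reflects the other treatment. It would enter a primary time point, and no later analysis could recover the uncontaminated value. The order of specimen collection and co-enrollment is a matter of trial conduct, so it has to be settled in the protocol.

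**Working it through.** **1. Dates**

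- Permitted Day 28 visit days: 28 to 28 + 4 = 32, that is 28, 29, 30, 31 and 32 (five days).
- First day on which another interventional study is allowed for a participant not hospitalized: Day 29.
- Overlap: Days 29, 30, 31 and 32, which is 4 of the 5 permitted days.
- Longest time on another treatment before the swab: 32 − 29 = 3 days.

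**2. Which outcomes are exposed**

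| Outcome or specimen | Tied to | Exposed? |
|---|---|---|
| Phase II NP swab, primary (Day 28 only) | in-person visit, to Day 32 | yes |
| Day 28 blood markers and stored samples | visit window, to Day 32 | yes |
| Symptom diary | study day 28 | no |
| Hospitalization or death, phase III primary | 28-day period | no |
| New Grade 3 or higher AE, primary | 28 days | no |
| Phase III nasal swab, secondary | self-collected at home | need not wait for the visit |

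**3. The plan's own power figure**

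Table 10.4.1-1 assumes 100 swabs per group, two-sided 5% and unpooled variance.

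SE = √[p₁(1 − p₁)/100 + p₂(1 − p₂)/100]; power = Φ(|p₂ − p₁|/SE − 1.96).

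- 40% v 60%: SE = √(0.0024 + 0.0024) = 0.0693; Φ(2.887 − 1.96) = 82.3%.
- 70% v 90%: SE = √(0.0021 + 0.0009) = 0.0548; Φ(3.651 − 1.96) = 95.5%.

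All seven rows of the table reproduce.

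**4. Illustration of size**

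The documents give no rate of co-enrollment on Days 29 to 32, so everything in this step is assumed. Suppose the true Day 28 percentages below LLoQ are 70% (placebo) and 90% (agent), and another treatment clears a share q of the swabs that would still have been quantifiable. An affected arm moves from p to p + (1 − p)q.

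| q | Both arms: difference, power | Placebo only: difference, power | Agent only: difference |
|---|---|---|---|
| 2% | 90.2 − 70.6 = 19.6 points, 95.0% | 90 − 70.6 = 19.4 points, 94.5% | 90.2 − 70 = 20.2 points |
| 5% | 90.5 − 71.5 = 19.0 points, 94.2% | 90 − 71.5 = 18.5 points, 92.7% | 90.5 − 70 = 20.5 points |
| 10% | 91 − 73 = 18.0 points, 92.6% | 90 − 73 = 17.0 points, 88.7% | 91 − 70 = 21.0 points |

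With 100 swabs per arm, q = 10% means 30 × 0.10 = 3 placebo swabs and 10 × 0.10 = 1 agent swab. The illustration treats Day 28 on its own. The primary test in 10.6.1 is a treatment-by-time interaction over four visits, of which one is exposed.

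**The case against.** The two co-enrollment provisions agree with each other and with the 28-day frame of the endpoints, so this is an overlap of dates and not a contradiction. Section 5.4.1 bars, while on study and before hospitalization, "any antibody-based therapy for COVID-19, remdesivir, fluvoxamine (unless used chronically") and several other named drugs, and that bar does not end at Day 28. Section 6.3.6 requires any approved or investigational agent thought active against COVID-19 to be recorded after entry, so an affected swab could often be identified. Section 4.3 also sends specific co-enrollment questions to the Study Management section.

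All of this stands, and it limits the weight of the point. It does not close the gap. Investigational agents outside the 5.4.1 list remain open, and those are what another trial might give. Recording a treatment identifies a contaminated swab without replacing it. Section 4.3 itself attaches no condition about the Day 28 evaluations.

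Three stronger readings are tempting, and the documents do not support them:

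- **That contamination would fall mainly on placebo and shrink the difference.** Nothing in the protocol says who would co-enroll on Days 29 to 32, or that persisting symptoms go with quantifiable RNA at Day 28. The illustration shows that the difference can move either way.
- **That phase III efficacy or the primary safety outcome is affected.** Both are bounded at 28 days, and the phase III swab is self-collected and secondary.
- **That 10.6.1 should exclude such swabs.** Section 10.6 is an outline and leaves detail to the SAP. Dropping swabs because of what participants did after randomization could also make the missing data informative.

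**Conclusion.** The point holds as a minor, cheaply corrected gap. Following the stated rules, the phase II Day 28 NP swab and the Day 28 blood samples may be collected after another trial's treatment has begun, on any of four of the five permitted visit days. One of the four primary virologic time points is exposed, by at most three days of other treatment.

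The effect is probably small. If another treatment cleared 2% to 10% of still-quantifiable swabs in both arms, power at Day 28 would fall from 95.5% to between 95.0% and 92.6%, under an assumed 70% v 90%. Those shares are assumptions, and neither frequency nor direction can be determined from the documents. The conclusion on dates needs no assumption beyond reading the plus-four-day cell as belonging to Day 28. Its place in the window row, after the Day 3 to 14 windows and before the Week 12 and 24 window, supports that reading.

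**What to change.** Reconcile 4.1.1.7, 4.3 and the Day 28 visit window by adding one clause to 4.3: a participant who co-enrolls in another interventional COVID-19 study from Day 29 completes the Day 28 specimen collection before the first intervention in that study. A cross-reference in 4.1.1.7 would keep the two sections aligned.

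The number of days on which treatment elsewhere can precede the Day 28 specimens then falls from four to none. Sample size and planned power do not change, and no visit is added. The cost falls only on participants who co-enroll in these days: the visit is moved forward within its window, or the first intervention elsewhere waits, by at most 32 − 29 = 3 days. No exclusion rule should be added to 10.6.1.

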5.0 INVESTIGATIONAL AGENT

Study treatment is defined as any active investigational agent and an appropriate placebo identified by the TOC for use in this study.

5.1 Regimen, Administration, and Duration

See relevant appendix/appendices for details of investigational agents.

5.2 Formulation, Storage, and Preparation

See relevant appendix/appendices for details of investigational agents.

5.3 Supply, Distribution, and Accountability

5.3.1 Acquisition/Distribution

See relevant appendix/appendices for details of investigational agents.

5.3.2 Accountability

See relevant appendix/appendices for details of investigational agents.

5.4 Concomitant Medications

Whenever a concomitant medication or investigational agent is initiated or a dose changed, investigators must review the concomitant medications and the relevant protocol appendix/appendices, as well as the most recent package insert, Investigator's Brochure, or updated information from DAIDS to obtain the most current information on drug interactions, contraindications, and precautions.

Additional drug information may be found on the ACTG Precautionary and Prohibited Medications Database located at http://tprc.pharm.buffalo.edu/home/di_search/.

5.4.1 Prohibited Medications

Use of hydroxychloroquine (unless used chronically for autoimmune diseases),

chloroquine (unless used for a parasitic infection), ivermectin (unless used for a parasitic infection), any antibody-based therapy for COVID-19, remdesivir, fluvoxamine (unless used chronically), and HIV protease inhibitors (unless used chronically for HIV infection) while on study, prior to hospitalization. In the event of hospitalization, these medications may be given unless otherwise specified in the agent-specific appendix/appendices.

See relevant appendix/appendices for additional prohibited medications, if applicable.

5.4.2 Precautionary Medications

See relevant appendix/appendices for precautionary medications, if applicable.

Phase II Evaluation	Screening	Study Entry/Day 0	Day 3	Day 7	Day 14	Day 28	Week 12	Week 24	Premature Study D/C (Before Day 28 Visit)	Premature Study D/C (After Day 28 Visit)
Visit Window			+/-1 day	+/-2 days		+4 days	-7/+14 days			
Participant-Completed Study Diary		Every Day through Day 28								
Study Diary Reminder		Days 1- 28								
Staff Review of Study Diary		X	X	X	X	X			X	
Retrieval of Study Diary						X			X	
Post-Acute COVID-19 Assessment							X	X		X
Household Infection and Linkage Report		X				X	X	X	X	X
Staff-Collected NP Swab		X	X	X	X	X			X	
Inflammatory Markers		X		X		X		X		
Coagulation Markers		X		X		X		X		
Hematology		Per Appendix for Investigational Agent								
Chemistry		Per Appendix for Investigational Agent								
Pregnancy Testing		Per Appendix for Investigational Agent								
Pharmacokinetics		Per Appendix for Investigational Agent								
Stored Plasma		X		X		X		X	X	X

Phase II Evaluation	Screening	Study Entry/Day 0	Day 3	Day 7	Day 14	Day 28	Week 12	Week 24	Premature Study D/C (Before Day 28 Visit)	Premature Study D/C (After Day 28 Visit)
Visit Window			+/-1 day	+/-2 days		+4 days	-7/+14 days			
Stored Serum		X		X		X		X	X	X
Stored PBMCs (Selected Sites)		X		X		X		X	X	

Table 6.1-2: Schedule of Evaluations Phase III

Phase III Evaluation	Screening	Study Entry/Day 0	Day 3	Day 7	Day 14	Day 28	Week 12	Week 24	Premature Study D/C (Before Day 28)	Premature Study D/C (After Day 28)
Visit Window			+/-1 day	+/-2 days		+4 days	-7/+14 days			
Documentation of SARS-CoV-2 Infection	X									
COVID-19 Symptom Screen	X	X								
Post-Acute COVID-19 Assessment							X	X		X
Medical/Medication History	X	X								
Smoking Status		X								
Clinical Assessments	X	X	X	X	X	X	X	X	X	X
Collect/Update Secondary Contacts		X	X	X	X	X	X			
Vital Status Check		If Participant Cannot be Reached per section 6.3.8								
Investigational Agent Administered	Per Appendix for Investigational Agent									
Study Kit Dispensed		X								
Participant-Completed Study Diary		Every Day through Day 28								
Study Diary Reminder		Days 1- 28								
Staff Review of Study Diary		X	X	X	X	X			X	
Retrieval of Study Diary						X			X	

Phase III Evaluation	Screening	Study Entry/Day 0	Day 3	Day 7	Day 14	Day 28	Week 12	Week 24	Premature Study D/C (Before Day 28)	Premature Study D/C (After Day 28)
Visit Window			+/-1 day	+/-2 days		+4 days	-7/+14 days			
Household Infection and Linkage Report		X				X	X	X	X	X
Self-Collected Anterior Nasal Swab		X	X	X	X	X			X	
Retrieval of Self-Collected Anterior Nasal Swabs			Follow Instructions in MOP						X	
Inflammatory Markers		X				X			X	
Coagulation Markers		X				X			X	
Hematology	Per Appendix for Investigational Agent									
Chemistry	Per Appendix for Investigational Agent									
Pregnancy Testing	Per Appendix for Investigational Agent									
Pharmacokinetics	Per Appendix for Investigational Agent									
Stored Plasma		X				X		X	X	X
Stored Serum		X				X		X	X	X

